Appendix A – Acthar (ACTH) Study Visit Schedule

| | SCR | OR | Day | | | | | | | | Week | | | | Month | | | | | | | | | | | | |
|--|-------|----|-----|---|----|----|----|----|----|----|------|---|---|---|-------|---|---|---|---|---|---|----|----|----|----|----|---|
| | -21-0 | 0 | 4 | 7 | 10 | 14 | 18 | 21 | 25 | 28 | 5 | 6 | 7 | 8 | 3 | 4 | 5 | 6 | 7 | 8 | 9 | 10 | 11 | 12 | 18 | 30 | |
| Informed consent | x | | | | | | | | | | | | | | | | | | | | | | | | | | |
| Background information | x | | | | | | | | | | | | | | | | | | | | | | | | | | |
| Inclusion/exclusion | x | | | | | | | | | | | | | | | | | | | | | | | | | | |
| Medical History | x | | | | | | | | | | | | | | | | | | | | | | | | | | |
| Transplant information | | x | | | | | | | | | | | | | | | | | | | | | | | | | |
| Pregnancy test | x | | | | | | | | | | | | | | | | | | | | | | | | | | |
| Vital signs | x | x | x | x | x | x | x | x | x | x | x | x | x | x | x | x | x | x | x | x | x | x | x | x | x | | |
| Physical exam | x | x | x | x | x | x | x | x | x | x | x | x | x | x | x | x | x | x | x | x | x | x | x | x | x | | |
| Laboratory tests *1 | x | x | x | x | x | x | x | x | x | x | x | x | x | x | x | x | x | x | x | x | x | x | x | x | x | | |
| Renal Biopsy | | x | | | | | | | | | | | | | x | | | | | | | | | | x | | |
| Study medication *2 | | x | x | x | x | x | x | x | x | x | x | x | x | x | x | x | x | x | | | | | | | | | |
| CD40 Ab *3 | x | | | | | | | | | | | | | | x | | | x | | | | | | | x | | |
| Follow-up (for secondary data on remission: yes or no) | | | | | | | | | | | | | | | | | | | | | | | | | | x | x |
| | | | | | | | | | | | | | | | | | | | | | | | | | | | |
| | | | | | | | | | | | | | | | | | | | | | | | | | | | |
| | | | | | | | | | | | | | | | | | | | | | | | | | | | |

*1 All laboratories (except CD40 Ab – see footnote *3) are part of SOC/Standard of Care. SOC labs include CBC, BMP, tacrolimus level, BK PCR plasma, CMV PCR plasma, DSA, Allosure and urine protein/creatinine.

*2 Study medication (Acthar) will continue twice a week through month 6 post-transplant.

*3 CD40 Ab which will be measured pre transplant, at 3, 6 and 12 months. This laboratory will be drawn at the same time as SOC labs so that patient does not have an additional blood drawn. [name] will assist with the testing of the CD40 Ab.

Figure 1

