The Use of Acthar (ACTH) in Patients with Focal Segmental Glomerulosclerosis (FSGS) Who Have Developed Chronic Kidney Disease Stage V (CKD) or End Stage Renal Disease (ESRD) and Are Undergoing a Renal Transplant

Principal Investigator: [name]., MPH
Ph. [contact]
Email: [contact]

COMIRB 17-2336

Version Date: July 11, 2018

I. Hypotheses and Specific Aims

This is an open-label pilot study where all subjects will be treated with the drug, Acthar. The specific aim is to determine the rate of recurrent FSGS through evaluation of kidney biopsies performed post renal transplantation. FSGS is a type of nephrotic syndrome that can recur aggressively after renal transplantation. When FSGS recurs after transplant it increases patient morbidity and increases graft loss.

It is believed that ACTH, besides steroid dependent properties, has steroid independent properties (see figure 1 on page 10). With the steroid independent properties it may stimulate the MCIR receptor which affects not only the podocytes, but also the T-cells, B-cells, NK-cells and APC-cells.

The primary end-point is to measure proteinuria prior (if patient still makes urine) and after renal transplantation and determine the change in proteinuria and the recurrence of FSGS as seen in kidney transplant biopsy. Kidney transplant biopsies will be performed at time 0 (at implantation), 3 months and 12 months post transplantation. Our hypothesis is that the use of Acthar, on patients with history of FSGS as cause of chronic kidney disease, at the time of renal transplantation and for a 6-month period of time following transplant, decreases the probabilities of patients developing recurrent disease after renal transplantation.

Our secondary end point is to evaluate renal function after transplantation as measured by eGFR. We hypothesize that patients will maintain a stable eGFR and creatinine while on Acthar and after it is stopped.

II. Background and Significance

Wait time for kidney transplantation is on average at least 5 years and unfortunately many patients die while waiting for kidney transplantation. Recurrent disease affects 23-30% of renal transplant recipients with FSGS. No

COMIRB 17-2336
P.I. [name]
Version 7-11-2018

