1. Renal transplant recipients whose primary disease is not FSGS

2. Patients who are receiving dual organ transplants
3. Patients who have been on Acthar prior to transplantation.
4. Intractable CHF (congestive heart failure)
5. Uncontrolled hypertension defined as BP >180/100
6. Uncontrolled diabetes defined as a HgbA1c>10%
7. An acute infection
8. Allergies to pig-derived proteins
9. Have received a live vaccine three months prior to transplant
10. Cushing's syndrome
11. Addison's disease
12. Previous intolerance to native ACTH or proteins of porcine origin
13. History of scleroderma, osteoporosis, systemic fungal infections, ocular herpes simplex, recent surgery, history of or the presence of peptic ulcer, primary adrenocortical insufficiency or adrenocortical hyperfunction.
14. Recent cardiovascular event within 3 months of screening including: Myocardial Infarction, CVA, TIA, New York Heart Association Functional Class III or IV failure, Obstructive valvular heart disease, or hypertrophic cardiomyopathy, second or third degree atrioventricular block not successfully treated with a pacemaker.
15. History of HIV
16. New diagnosis of cancer or recurrent cancer within 2 years of screening
17. History of alcohol or drug abuse within 12 months of study entry.
18. Receipt of any investigational drug within 30 days of enrollment.
19. Psychiatric disorder that interferes with the patient's ability to comply with the protocol.
20. Poorly controlled diabetes with an HbA1C > 10%
21. Type 1 diabetes mellitus
22. Pregnancy

D. Treatment Overview

Screening will be performed by the Principal Investigator during the kidney transplant evaluation clinics and during the wait list kidney transplant evaluation clinic. All patients with FSGS will have induction therapy with thymoglobulin and maintenance immunosuppression with tacrolimus and mycophenolate. This is the standard regimen that we utilize post transplant in all our recipients.

E. Dosage and Administration of Acthar

The dose of Acthar to be given to every enrolled patient will be 80 units twice a week for 6 months. The first dose of Acthar is given at the time of transplantation and will be continued, twice a week, for 6 months. See Appendix A (page 9) for additional details.

Safety:

1. Acthar should always be injected beneath the skin or into the muscle.
2. Never inject Acthar directly into a vein.

Risks:

1. Development of high blood sugars (10%)
2. Development of high blood pressure (11%)
3. Edema (1%)

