4. Mood and behavior changes (7%)
5. Weight and appetite changes (1%)

We will be monitoring all patients at the stated time points for all the above risks and side effects. We will be monitoring side effects with our research transplant coordinator and the PI who will be seeing the patients. We will also have a safety officer, [name], who will be reviewing the adverse events. At every clinic visit, as standard of care, patients get their vital signs taken as well as urinalysis and laboratories. We will be reviewing all the results carefully and assess every patient to see if there are any signs of infection. [name] will also be part of the DSMB. While [name] will review safety data and adverse events every three months, the DSMB, of which she will be a member, will meet every 12 months.

F. Laboratory Testing and Study Schedule

Patients will have one pre-transplant serum sample which will be measured for CD40 Ab. A 2nd blood sample will be obtained at 3 months post transplant, 6 months post transplant and at 1 year post transplant. This blood will be drawn with standard of care labs, so it would not impose additional blood draws to the patient.

Standard of care labs include CBC, BMP, tacrolimus level, BK PCR plasma, CMV PCR plasma, DSA, Allosure testing and urine protein/creatinine.

- The first month post transplant, patients will have labs and clinic visit biweekly.
- The second month post transplant patients will have labs and clinic visit weekly.
- The third month post transplant patient will have labs weekly and clinic visit every other week.
- From the 4th till the 6th month post transplant patients will have labs every other week and clinic visit monthly.

- From month 6 till month 12 patients will have labs monthly and clinic visit every other month.

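### Pregnancy stops treatment, but Appendix A schedules a pregnancy test only at screening and none at the 16 study-medication visits after day 0

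*Combined protocol and SAP*

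**What the plan says.** Pregnancy appears twice as a criterion: item 22 of the exclusion list in Section III.C and item 5 of the stopping criteria in Section III.I.

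Appendix A gives the pregnancy test its own row, "Pregnancy test | x", with a single mark under the -21-0 screening column. The treatment row begins "Study medication *2 | | x | x" and is marked from day 0 to month 6. Section III.E sets the dose at "80 units twice a week for 6 months" and states that "The first dose of Acthar is given at the time of transplantation". Footnote *2 to Appendix A agrees: "Study medication (Acthar) will continue twice a week through month 6 post-transplant".

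The recurring laboratory panel is described in footnote *1: "SOC labs include CBC, BMP, tacrolimus level, BK PCR plasma, CMV PCR plasma, DSA, Allosure and urine protein/creatinine". It names no pregnancy test, and neither do the laboratory list in Section III.F or the list of data taken from the medical record in Section III.G.

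**The concern.** A stopping rule works only as fast as the condition is recognised. For severe hypertension, the measurement that triggers the stop (vital signs) is marked at every dosing visit. For pregnancy, the protocol provides a specific test and uses it once, to establish eligibility, although the stopping rule makes pregnancy status matter for the next six months.

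The inclusion criteria admit adults with no limit on sex or upper age, and the exclusion and the screening test show that women who could become pregnant are expected. At stake is late recognition: a woman who became pregnant after screening could go on receiving a drug that the protocol says should be stopped.

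**Working it through.** The plan gives no figure of its own on this point, and its power and confidence-interval calculations are not involved. The check is a count of Appendix A marks and some arithmetic on the dosing calendar.

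**Marks in Appendix A**

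| Row | Marks from day 0 to month 6 | Where |
|---|---|---|
| Study medication | 1 + 8 + 4 + 4 = 17 | day 0; days 4, 7, 10, 14, 18, 21, 25, 28; weeks 5–8; months 3–6 |
| Physical exam, vital signs, laboratory tests | 17 each | the same visits |
| Pregnancy test | 0 | its only mark is in the screening column |

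The screening window runs to day 0, so the one scheduled test may fall on the day of the first dose. Day 0 is therefore not counted as untested, which leaves 17 − 1 = 16 visits after the first dose, none with a test. In the text copy of the table, some marks later than month 6 sit one column to the right (the 12-month biopsy, for example). The columns used here are aligned: the 3-month biopsy and the 3- and 6-month CD40 samples fall where the text puts them.

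**Length of the untested period**

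- Six months taken as 26 weeks: 26 × 7 = 182 days.
- Doses: 26 × 2 = 52 (24 × 2 = 48 if a month is taken as four weeks).
- Worst case since the last test, reading -21 as days, with screening on day -21 and no repeat at day 0: 182 + 21 = 203 days.

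**Effect of the proposed tests**

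Assume evenly spaced doses on day 3.5 × k, with k = 0 to 51, and months of 30.44 days, so that months 3, 4 and 5 fall on days 91.3, 121.8 and 152.2.

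| Test | Day | Days since previous test | Doses on or after this day |
|---|---|---|---|
| Day 0 or screening that day | 0 | – | 52 |
| Day 28 | 28 | 28 | 44 |
| Week 8 | 56 | 28 | 36 |
| Month 3 | 91.3 | 35.3 | 25 |
| Month 4 | 121.8 | about 30.4 | 17 |
| Month 5 | 152.2 | about 30.4 | 8 |

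The stretch from month 5 to the end of dosing is 182 − 152.2 = 29.8 days. The longest interval is 35.3 days, from week 8 to month 3, and spans 36 − 25 = 11 doses. A month-6 test would have no doses ahead of it, so it is not proposed.

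**The case against.** The best defence is that a stopping criterion does not require its own scheduled test. Heart failure and severe edema are on the same list without one and are acted on when recognised clinically. Physical examination is marked at all 17 dosing visits, and Section III.J has adverse events monitored weekly. Section III.E adds coordinator and investigator contact and a three-monthly safety review, and says "At every clinic visit, as standard of care, patients get their vital signs taken as well as urinalysis and laboratories". The wording of footnote *1 does not make the laboratory list exhaustive, so a test could be ordered in routine care. The consent pages are not in the public copy and may set contraception or reporting duties.

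Much of this stands, and it rules out several stronger readings that a reader might infer:

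- *That nothing during dosing could reveal a pregnancy.* The examinations and adverse-event monitoring might. What is missing is a scheduled test.
- *That all 17 dosing visits are untested.* The screening test may be done on day 0.
- *That the protocol contradicts itself, or neglects contraception.* A stop on recognition is coherent, and contraception advice cannot be judged without the consent pages.
- *That pregnancies are likely, or that a particular harm would follow.* The documents give no pregnancy rate, no count of eligible women and no account of Acthar in pregnancy.

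None of this puts a test into Appendix A after screening. It is also fair to say that the documents prescribe no testing interval; roughly monthly is a judgement. The dose counts measure exposure between tests, not risk.

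**Conclusion.** The point holds as a gap in safety monitoring. A condition that requires treatment to stop has no scheduled test at any of the 16 study-medication visits after day 0, over about 182 days and about 52 doses. The mark count rests on Appendix A alone. The day and dose figures assume 26 weeks of evenly spaced twice-weekly dosing. How many participants are affected is unknown. Proteinuria, recurrence, eGFR and their analyses are untouched. The change is worth making because it is cheap and supports a rule the protocol already contains; it does not correct a flaw in validity.

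**What to change.** In the pregnancy-test row of Appendix A, for women who could become pregnant, mark:

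- day 0, if the screening test was done on an earlier day;
- day 28, week 8, and months 3, 4 and 5.

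Use blood or urine already collected at those visits. Section I qualifies the pre-transplant proteinuria measurement with "if patient still makes urine", so specify blood at day 0 for a patient without urine output.

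Add a footnote that these tests are required by the study. Footnote *1 now classes every laboratory test except CD40 Ab as standard of care, so the amendment should also settle who pays.

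The cost is one amendment, no extra visits, and 5 to 6 inexpensive tests per eligible woman. The number of eligible women is not given: if 2 to 8 of the 20 were eligible (an assumption), the total would be 5 × 2 = 10 to 6 × 8 = 48 tests, and it cannot exceed 6 × 20 = 120. The clinical downside is that a false positive could hold a dose until the test is repeated.
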